Objectives	Initial Cohort To document performance of the MANTIS TM Clip in all indications for endoscopic clipping.					
	Continued Enrollment Cohort To evaluate the procedural and clinical merit in consecutive cases in which at least one MANTIS clip is selected, of specific attributes of the MANTIS TM Clips, including but not limited to the ability of this new endoscopic clipping device:					
	o to provide prophylaxis to reduce the risk of delayed bleeding post lesion resection					
	 to close post mucosal resections/polypectomy ulcers, post submucosal dissection ulcers, or mucosal incisions made in conjunction with endoscopic myotomy procedures 					
	o to close lumenal perforations, fistulas, or leaks					
	o to close perforations after full thickness resection of lesions in the gastrointestinal (GI) tract					
Indications for Use	Resolution TM Clip family is indicated for clip placement within the GI tract for the purpose of:					
	1. Endoscopic marking					
	2. Hemostasis for:					
	 Mucosal/sub-mucosal defects < 3 cm 					
	o Bleeding ulcers					
	o Arteries < 2 mm					
	o Polyps < 1.5 cm in diameter					
	Diverticula in the colon					
	 Prophylactic clipping to reduce the risk of delayed bleeding post lesion resection 					
	3. Anchoring to affix jejunal feeding tubes to the wall of the small bowel					
	4. As a supplementary method, closure of GI tract luminal perforations < 20 mm that can be treated conservatively					

Page 3 of 40					
	MANTIS Clip Study				
Study Device	dy Device MANTIS TM is a clip in the Resolution 360 Clip product family.				
Study Procedure	The portion of the endoscopic procedure where the MANTIS TM Clip is used for hemostasis, closure, anchoring or marking.				
Study Design	Prospective, multi-center, open label, consecutive enrollment Group A: Hemostasis Group B: Closure Group C: Anchoring Group D: Endoscopic Marking Group E: Other				
Number of Subjects and Sites	 Initial Cohort: Up to 50 cases Continued Enrollment Cohort: 240 cases Up to 15 sites globally 				
Primary Effectiveness Endpoint	Initial Cohort Ability to complete the indication for the use of endoscopic clipping Continued Enrollment Cohort Clinical success defined as, where applicable, Absence of delayed bleeding Sustained closure of the targeted leasion up to 30 days after the endoscopic clipping procedure				
Primary Safety Endpoint Rate of serious adverse events (SAEs) related to the MANTIS TM clip or the endoscopic study portion of the procedure. NOTE: If providing hemostasis to an active bleed requires possible additional hemostasis after the index study procedure for management of bleeding SAEs within 7 days ³⁶ of the index study procedure, then such bleeding SAEs are not counted for the Primary Safety Endpoint.					
Additional Endpoints	 Technical success at placement defined as ability to deploy the endoscopic clips in satisfactory position. Ability to anchor device, mobilize the tissue, and approximate defect edges for secured closure. (Group B only). 				

MANTIS Clip Study 3. Post procedural bleeding, defined as a severe bleeding event that required hospitalization, a blood transfusion (>5 units), or another invasive intervention (angiographic or surgery) within 30 days after the study clip placement. 4. For active bleeding hemostasis cases only a. Rate of patients requiring additional modalities of hemostasis. b. Report of hemostasis of active bleeding 7 days after the index study procedure, defined as ability to stop the active bleed at the time of the study procedure and/or with additional clipping procedures to provide hemostasis of continued or recurrent bleeding within 7 days of the index study procedure Follow-up Baseline Schedule Procedure 30 day follow up (both Initial and Continued Enrollment Cohort) **Study Duration** Enrollment is expected to be completed in approximately 12 months; therefore the total study duration is estimated to be approximately 13 months as Subjects will be on the study for up to 30 days. **Key Inclusion** 1. Subject indicated for endoscopic clipping per local standard of Criteria practice. 2. Willing and able to comply with the study procedures and provide written informed consent to participate in the study. NOTE: Hemostasis and closure can be needed in the setting of complications such as perforations or acute bleeding that are typically rare and sometimes emergent. In such circumstances consenting the patient before the procedure is not feasible and consent shall be obtained from the patient after the procedure but before any study data is collected. **Kev Exclusion** 1. Subjects who are currently enrolled in another investigational study Criteria that would directly interfere with the current study, without prior written approval from the sponsor. 2. Subjects who the investigator deems at risk for study device or procedure related complications per the Instructions for Use (IFU), where commercially available or the Investigator Brochure (IB) for countries where the study device is not approved.

MANTIS Clip Study

Statistical Methods

Initial cohort:

No hypotheses will be tested, only observational, summary statistics will be performed.

Continued enrollment cohort:

A systematic literature search was conducted on PubMed and Embase from January 1, 2016 to September 2022 to identify studies that evaluated the safety and effectiveness of an endoscopic clip device for closing various types of incisions, lesions, or defects in the gastrointestinal tract resulting from endoscopic mucosal resection (EMR), endoscopic submucosal dissection (ESD), polypectomy of polyps or adenomas, perforations, and fistulas. The primary objective of the search strategy was to identify studies that examined the closure of large mucosal defects by endoscopic clipping. Twenty studies were identified through a post-market literature review activity were included to the analysis with a total of 2257 patients.

We hypothesize that the **clinical success rate** of MANTISTM clip will be greater than the performance goal of **89%** with expected clinical success rate of **94%**. These assumptions are based in the following meta-analyses of clinical success for closure of a defect:

• 20 publications representing 2257 patients: 93.9% (95% CI 88.6%-97.6%)

We hypothesize that the **serious adverse event (SAE) rate** related to MANTISTM clip or the endoscopic clipping portion of the procedure will be lower than the performance goal of **19%** with expected related SAE rate of **10%**. These assumptions are based in the following meta-analyses of clinical success for closure of a defect:

9 publications representing 1019 patients: 9.8% (95% CI 3.7%-18.5%)

Using an exact test with an alpha level of 0.05, **240 subjects** enrolled will provide at least 80% power for the performance and safety metrics. These tests will only be performed for cases in the continued enrollment cohort.

3. Table of Contents

1.	TITL	E PAGE	1
2.	Pro	TOCOL SYNOPSIS	4
3.	TAB	LE OF CONTENTS	8
	3.1.	Table of Figures	11
	3.2.	Table of Tables	11
4.	Intr	ODUCTION	12
	4.1.	Background	12
	4.2.	Study Rationale	13
5.	DEV	ICE DESCRIPTION	13
	5.1.	Device Under Study	13
6.	STUI	DY OBJECTIVES	14
7.	STUI	DY ENDPOINTS	15
	7.1.	Primary effectiveness endpoints	15
	7.2.	Primary Safety endpoint	15
8. S	TUDY	DESIGN	16
	8.1	Scale and Duration	16
	8.2	Justification for the Study Design	16
9	SUBJ	ECT SELECTION	17
	9.1	Inclusion Criteria	17
	9.2	Exclusion Criteria	17
10	SUBJ	ECT ACCOUNTABILITY	17
	10.1	Point of Enrollment	17
	10.2	Withdrawal	18
	10.3	Lost to Follow-Up	18
	10.4	End-of-Study Definition	18
11	STUI	DY METHODS	19
	11.1	Data Collection	19
	11.2	Study Candidate Screening	19

Confidential

4.1. Background

The endoscopic clip, endoclip or hemoclip, was first introduced by Hayashi for the treatment of gastrointestinal (GI) bleeding in Japan in 1975. Over the past decades, the hemostatic clips technology has evolved and it has become the standard of care for gastrointestinal bleeding. Endoscopic clips achieve gastrointestinal hemostasis by clamping the vessel and/or approximating the edges of the lesion, producing mechanical compression without causing tissue injury.^{2,3}

Gastrointestinal bleeding (GIB) is one of the major causes of emergency hospital admission. In the United States, GIB accounted for more than 500,000 hospitalizations and consumed nearly US\$5 billion in 2014.4 GIB is usually categorized according to its anatomic location as either upper GIB (UGIB) or lower GIB (LGIB). Acute UGIB may originate in the esophagus, stomach, and duodenum. The common causes of acute UGIB are peptic ulcer disease including from the use of aspirin and other non-steroidal anti-inflammatory drugs, variceal hemorrhage, Mallory-Weiss tear and neoplasms including gastric cancers. Other relatively common causes include esophagitis, erosive gastritis/duodenitis, vascular ectasias and Dieulafoy's lesion.⁵ Among 16%-20% of acute UGIB cases, more than one endoscopic diagnosis may be identified as the cause of GIB. Acute UGIB is a common condition worldwide that has an estimated annual incidence of 40-150 cases per 100,000 population, frequently leads to hospital admission, and has significant associated morbidity and mortality, especially in the elderly.⁶ LGIB is defined as bleeding that emanates from a source distal to the ligament of Treitz. LGIB is approximately one-fifth as common as UGIB and accounts for approximately 20 to 30 hospitalizations per 100,000 adults per year. The incidence of LGIB increases substantially with age, presumably due to the high incidence of diverticulosis and vascular disease in this group. Prognosis in LGIB varies and given that most acute LGIB is self-limited, outcomes are typically favorable. However, the mortality associated with LGIB is generally considered to be less than 5% and when it occurs, is often a result of comorbid condition.⁷

UGIB usually presents with hematemesis and/or melena. Hematochezia usually indicates bleeding from the lower GI tract but can occasionally be the presentation for a briskly bleeding upper gastrointestinal source. Variceal hemorrhage is life threatening and should be a major consideration in diagnosis as it accounts for up to 30% of all cases of acute UGIB and up to 90% in patients with liver cirrhosis. LGIB classically presents with hematochezia, however bleeding from the right colon or the small intestine can present with melena. Bleeding from the left side of the colon tends to present bright red in color, whereas bleeding from the right side of the colon often appears dark or maroon-colored and may be mixed with stool.⁵

Following the publication of Hayashi et al, Binmoeller KF et al popularized the endoclip use in 1993 by conducting an uncontrolled study to evaluate performance of an improved metallic clip (Olympus hemoclip) for the endoscopic treatment of nonvariceal GIB.⁸ Initial designs were cumbersome and performed inconsistently. Improvements appeared in the mid-1990s from the Olympus Company with the introduction of a reloadable clip. It was reusable rotatable device that required manually reloading a disposable clip onto a small hook at the end of a metal cable running through a plastic sheath. Followed by the pre-loaded QuickClip in 2002

and rotatable QuickClip2 in 2005. The preloaded version is easier and faster to use, especially in the setting of a bleeding lesion. Cook's TriClip and Boston Scientific's Resolution clip both were launched in 2003. At the end of 2010, a new type of clip, developed by Ovesco Endoscopy AG as an over-the-scope-clip device and commonly known as the bear claw, was introduced. Its design was fundamentally different from through-the-scope devices in that the clip is held on the outside of the tip of the endoscope until it is released, by a deployment much like a band-ligation handle. ^{9, 10} A new clip by Cook Medical was introduced on a limited basis in the United States in 2011. The Instinct Endoscopic Hemoclip has similarities and differences from its predecessors. It has two arms with anchoring teeth and nitinol strips for added strength, controlled 360-degree bidirectional rotation, no plastic sheath, can be opened and closed multiple times and has a very simple, one-directional deployment mechanism. Resolution 360™ Clip was launched by Boston Scientific Corporation, and CE marked in December 2016 with the features such as controlled 360-degree bidirectional rotation, radiopacity and MR conditional.

This overtime improvement in design and performance of endoclip devices resulted in use of hemostatic clips for variety of GIB conditions such as prevention of bleeding from ulcers¹¹, Mallory Weiss tears ¹², Dieulafoy's lesion¹³, polypectomy sites¹⁴, varices¹⁵⁻¹⁷, and diverticulae¹⁸; to close mucosal defects resulting from endoscopic mucosal resection¹⁹, hemostasis of GI fistula²⁰; and perforations of the esophagus²¹, stomach²², and colon²³. Clips have also been used to secure feeding tubes²⁴, esophageal stents, and manometry catheters to the GI wall. Endoscopic clipping using the currently available devices appears effective and safe.²⁵⁻³³

4.2. Study Rationale

The MANTIS Clip is designed to be delivered Through-The-Scope (TTS) and has features intended to optimize ability to close mucosal/submucosal defects by anchoring the device, mobilizing the tissue, and approximating defect edges for secure closure. This clinical study aims to document in a prospective manner the use of the MANTIS TTS clip and the impact of its enhanced capabilities when used for hemostasis, closure, anchoring and marking. Compared to prior endoscopic clips in the Resolution 360 Platform the MANTISTM clip has newly designed jaws which have increased jaw thickness and modified teeth geometry aimed to provide enhanced tissue grasping capabilities.

This study will prospectively document the performance of the MANTIS clip when used per standard of practice. It is designed to be a multicenter study to assure broad representation of use of the MANTIS clip.

5. Device Description

5.1. Device Under Study

The MANTIS™ clip, which is manufactured by Boston Scientific Corporation is a Through-The-Scope (TTS) device that leverages all features and advantages on the delivery system and the deployment system from the Resolution 360 product family.

[figure not shown]
The MANTIS Clip is indicated for clip placement within the Gastrointestinal (GI) tract for the purpose of Endoscopic marking, Hemostasis for: Mucosal/sub-mucosal defects < 3 cm, Bleeding ulcers, Arteries < 2 mm, Polyps < 1.5 cm in diameter, Diverticula in the colon, Prophylactic clipping to reduce the risk of delayed bleeding post lesion resection, Anchoring to affix jejunal feeding tubes to the wall of the small bowel, and as a supplementary method, closure of GI tract luminal perforations < 20 mm that can be treated conservatively.

The MANTIS clip consists of a radiopaque, single-use clip with an 11mm clip opening, preloaded on a flexible, rotatable delivery system. The clip is designed to be compatible with forward viewing endoscopes with working channels equal to or greater than 2.8 mm.

The radiopaque MANTIS clip is engineered to enable opening and closing no more than five times prior to deployment, aiding in repositioning of the clip at the lesion site. Re-opening, closing and rotation capability may be limited by clinical circumstances and patient anatomy, among other factors.

Study devices are labeled on the box and inner pouch and include information not limited to name of legal manufacturer, device name and dimensions, lot number and expiration date. Device labeling will be provided in local language(s) as per national regulations. For a detailed description of each device, please reference the Instructions for Use (IFU) included in each device package where commercially available or the Investigator Brochure (IB) for countries where the study device is not approved.

Figure 1. Jaw geometry comparison (full and augmented view) Resolution 360 (left) vs MANTISTM clip (Right)

6. Study Objectives

Initial Cohort:

To document performance of the MANTISTM Clip in all indications for endoscopic clipping.

Continued Enrollment Cohort:

To evaluate the procedural and clinical merit in consecutive cases in which at least one MANTIS clip is selected, of specific attributes of the MANTISTM Clips, including but not limited to the ability of this new endoscopic clipping device:

- o to provide prophylaxis to reduce the risk of delayed bleeding post lesion resection
- to close post mucosal resections/polypectomy ulcers, post submucosal dissection ulcers, or mucosal incisions made in conjunction with endoscopic myotomy procedures
- o to close lumenal perforations, fistulas, or leaks
- o to close perforations after full thickness resection of lesions in the gastrointestinal (GI) tract

7. Study Endpoints

7.1. Primary effectiveness endpoints

Initial Cohort

Ability to complete the indication for the use of endoscopic clipping

Continued Enrollment Cohort

Clinical success defined as, where applicable,

- Absence of delayed bleeding
- Sustained closure of the targeted leasion (up to 30 days after the endoscopic clipping procedure)

7.2. Primary Safety endpoint

Rate of serious adverse events (SAEs) related to the MANTISTM clip or the endoscopic study portion of the procedure.

NOTE: If providing hemostasis to an active bleeding in Group A requires possible additional hemostasis after the index study procedure for management of bleeding SAEs within 7 days of the index study procedure, then such bleeding SAEs are not counted for the Primary Safety Endpoint.

Additional endpoints:

- Technical success at placement defined as ability to deploy the endoscopic clips in satisfactory position.
- Ability to anchor device, mobilize the tissue, and approximate defect edges for a secured closure.
- Post procedural bleeding, defined as a severe bleeding event that required hospitalization, a blood transfusion (>5 units), or another invasive intervention (angiographic or surgical) within 30 days after completion of the study clip placement procedure.

- For active bleeding hemostasis cases only
 - o Rate of patients requiring additional modalities of hemostasis.
 - Report of hemostasis of active bleeding 7 days after the index study procedure, and/or with additional clipping procedures to provide hemostasis of continued or recurrent bleeding within 7 days of the index study procedure

8. Study Design

Prospective, multi-center, multi-national, open label, consecutive enrollment. The population will be split up into 5 groups, namely:

- Group A: Hemostasis
- Group B: Closure
- Group C: Anchoring
- Group D: Endoscopic Marking
- Group E: Other

8.1 Scale and Duration

Scope of the series:

- Initial Cohort:
 - o Up to 50 cases
- Continued Enrollment Cohort:
 - o Up to 240 cases not including Initial Cohort
- Up to 15 sites

The study duration for each subject is expected to be approximately 1 month. Enrollment is expected to be completed in approximately 18 months per cohort.

Study visits:

- Screening/Enrollment and Baseline: Informed consent process, including informed consent signature date
- Procedure
- 30-day follow-up Telephone Interview

8.2 Justification for the Study Design

The study is designed to demonstrate that physicians are able to complete standard of care procedures using of a new endoscopic clipping device when used for hemostasis, closure, anchoring and marking.

9 Subject Selection

9.1 Inclusion Criteria

Subjects who meet all of the following criteria (see Table 9.1-1) may be given consideration for inclusion in this clinical investigation, provided no exclusion criterion (see Section 9.2) is met.

Table 9.1-1: Inclusion Criteria

Inclusion Criteria

- 1. Subject indicated for endoscopic clipping per local standard of practice.
- 2. Willing and able to comply with the study procedures and provide written informed consent to participate in the study

NOTE: Hemostasis and closure can be needed in the setting of complications such as perforations or acute bleeding that are typically rare and sometimes emergent. In such circumstances consenting the patient before the procedure is not feasible and consent shall be obtained from the patient after the procedure but before any study data is collected.

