10.1 Point of Enrollment

Subjects will be considered enrolled into the study at the time of the study-specific Informed Consent Form (ICF) execution. Subjects who have signed informed consent but do not undergo the study procedure are considered screen failures. Screen failures will be recorded

in the Electronic Data Capture (EDC) system by each study site and will not count toward total study enrollment.

In the case it is determined that the subject failed to meet the inclusion/exclusion criteria after the subject has agreed to participate in the study and has signed the informed consent, the study personnel will complete the Screening form and the End of Study form.

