11.2 Study Candidate Screening

No study-specific data will be collected until after the subject has signed an Informed Consent Form (ICF). A Screen Failure/Enrollment Log will be maintained in the EDC system by the center to document select information about candidates who signed consent.

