19.6 Reporting to Regulatory Authorities / IRBs / ECs / REBs/ Investigators

BSC is responsible for reporting adverse event information to all participating Principal Investigators, IRBs/ECs/REBs and regulatory authorities, as applicable.

The Principal Investigator is responsible for informing the IRB/EC/REB, and regulatory authorities of UADEs/USADEs and SAEs as required by local/regional regulations.

20 Informed Consent

Subject participation in this clinical study is voluntary. Informed Consent is required from each subject or his/her legally authorized representative. NOTE: Hemostasis and closure can be needed in the setting of complications such as perforations or acute bleeding that are typically rare and sometimes emergent. In such circumstances consenting the patient before the procedure is not feasible and consent shall be obtained from the patient after the procedure but before any study data is collected.

The Principal Investigator may enroll a subject without obtaining the informed consent of the subject or his/her legally authorized representative only when the following conditions are fulfilled.

- The prospective subject fulfils the emergency conditions and is obviously in a life-threatening situation.
- o There is a fair possibility that the life-threatening risk to the prospective subject can be avoided if the device is used.
- Anticipated risks are outweighed by the potential benefits of applying the device.
- The legally authorized representative cannot be promptly reached and informed.

In either situation, arrangements shall be made to inform the subject or legally authorized representative as soon as possible about a) all aspects of the clinical study and b) the subject's inclusion in the clinical study.]

The obtaining and documentation of Informed Consent must be in accordance with the principles of the Declaration of Helsinki, ISO 14155, any applicable national regulations, and local Ethics Committee and/or Regulatory authority, as applicable. The ICF must be accepted by BSC or its delegate (e.g. CRO), and approved by the site's IRB/EC/REB, or central IRB, if applicable.

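### Emergency cases may sign consent after the clip result is known and only signers are logged, so entry to the consecutive cohort can depend on early outcome and the plan could not show whether it did

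*Protocol*

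**What the plan says.** - **Consent timing.** The note to the inclusion criteria (Protocol 9.1, repeated in the synopsis, in Section 20 and in SAP Section 1) covers perforation and acute bleeding where prior consent is not feasible. In those cases "consent shall be obtained from the patient after the procedure but before any study data is collected".
- **Point of enrolment.** Protocol 10.1: "Subjects will be considered enrolled into the study at the time of the study-specific Informed Consent Form (ICF) execution". Section 11.4 repeats this and bars data collection before signature.
- **Log.** Protocol 11.2: "A Screen Failure/Enrollment Log will be maintained in the EDC system by the center to document select information about candidates who signed consent".
- **Analysis sets.** In Protocol 12.2.1 and SAP 4.1 the ITT cohort is drawn from enrolled subjects, and the Treated cohort is a subset of ITT.
- **Cohort claim.** Protocol Section 6 describes the Continued Enrollment Cohort as "consecutive cases in which at least one MANTIS clip is selected".
- **Other consent routes.** Section 20 states that "Informed Consent is required from each subject or his/her legally authorized representative". It also states that "The Principal Investigator may enroll a subject without obtaining the informed consent of the subject" or of a representative when listed life-threatening conditions hold, and that "arrangements shall be made to inform the subject or legally authorized representative as soon as possible".

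**The concern.** The only bound on post-procedure consent is that it precede data collection. Data collection itself waits for signature, so the bound sets no deadline. By the time such a patient is asked, the operator knows the immediate result of the clip and perhaps the first days of its course. A patient who does well can still sign. A patient who re-bleeds, goes to surgery or dies first may never sign, and then no analysis set contains that patient.

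Both primary endpoints are tested in a single arm against a fixed goal, so no control arm shares the distortion. Missing failures raise the observed success rate, and missing related-SAE patients lower the observed SAE rate. Both errors favour the device. The plan requires no count of the procedures at which a MANTIS clip was selected, so a reader of the final report could not judge how complete the consecutive series was.

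**Working it through.** **1. Reproduce the plan's figure.** Inputs from Protocol 12.1.1.3 and SAP 3.1.3: success goal 89%, expected 94%, exact test, alpha 0.05, 217 analysed, 240 enrolled. The hypotheses in SAP 3.1.3 are one-sided.

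- Pass rule: the smallest r with P(X ≥ r | 217, 0.89) ≤ 0.05. This gives r = 201, with exact type I error 4.9% (r = 200 would give 7.9%).
- Power: P(X ≥ 201 | 217, 0.94) = 84.1%, consistent with the stated 80% or more.
- At one-sided 0.025 the power would be 67.6%, so one-sided 0.05 is the reading that reproduces the plan.

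**2. Follow a non-signer through the plan.**

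| Step | Rule | Result for a non-signer |
|---|---|---|
| Enrolment (10.1, 11.4) | starts at ICF signature | not enrolled |
| Log (11.2) | signers only | not logged |
| ITT and Treated (12.2.1; SAP 4.1) | subsets of enrolled | not analysed |
| Withdrawal and loss to follow-up (10.2, 10.3) | apply after enrolment | not counted |

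**3. Size, by assumption.** The documents give no share of emergency or post-procedure-consent cases. Let e be the emergency share of cases, q the failure rate among them, and m = 0.5 the fraction of those failures that never sign. The overall true success rate is held at 89%, so a pass is a false pass.

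- Fraction of all cases lost = e × q × m
- Expected observed success = 0.89 / (1 − e × q × m)
- False-pass probability = P(X ≥ 201 | 217, observed success)

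| e | q | Cases lost | Observed success | False pass |
|---|---|---|---|---|
| none lost | – | 0 | 89.0% | 4.9% |
| 5% | 20% | 0.50% | 89.4% | 7.4% |
| 5% | 30% | 0.75% | 89.7% | 8.9% |
| 10% | 20% | 1.00% | 89.9% | 10.8% |
| 10% | 30% | 1.50% | 90.4% | 15.4% |

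For 217 analysed, the missing failures number 217 × lost / (1 − lost): about 1.1 in the mildest row and 3.3 in the most severe.

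**4. Fragility at the planned result.** The expected 94% of 217 is 204 successes, for which P(X ≥ 204 | 217, 0.89) = 0.008. Adding unseen failures to the denominator:

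- three more: 204/220, p = 0.043
- four more: 204/221, p = 0.066, no longer significant
- thirteen more: 204/230 = 88.7%, below the goal

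**The case against.** Several points on the other side stand.

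- **Selection is permitted, not shown.** A reader might infer that the cohort is in fact selected on outcome. The documents do not support that. Section 11.3 says all patients under an investigator's care are to be considered for recruitment, and Section 9.1 calls these complications typically rare.
- **There are other routes in.** Section 20 allows a representative to sign, with the subject's own consent sought later, and allows enrolment without consent in narrow life-threatening circumstances. A ventilated patient is therefore not automatically excluded. However, Section 9.1 says consent comes from the patient, and Sections 10.1 and 11.4 make signature the point of enrolment. None of these provisions sets a latest time for signature or counts non-signers.
- **Some trace may exist.** A reader might infer that non-signers leave no record anywhere. That goes too far. Section 15.1 requires use records for investigationally labelled clips, and Section 16.2 requires records where commercial product is supplied free. These records do not reach purchased commercial clips, and no reported denominator is built from them.
- **Larger effects are tempting.** If 10% or 30% of all failures went unseen, the false-pass probability would be 11.6% or 43.6%. But the mechanism acts only on post-procedure consents. Losing 30% of all failures means losing 0.30 × 11% = 3.3% of cases. If emergencies are 10% of cases, that needs a 33% emergency failure rate with none of those patients signing; at 5% it needs 66%.
- **Safety is partly shielded.** In active-bleed cases, bleeding SAEs managed with additional hemostasis within 7 days are not counted. Perforation, other related SAEs and the effectiveness endpoint have no such shield.
- **A consent cut-off could backfire.** It might exclude the sickest patients, who could sign only after recovery.

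**Conclusion.** The concern holds in a limited form. Followed exactly, the plan cannot support its claim to a consecutive series. Entry can depend on early outcome in post-procedure-consent cases, non-signers appear in no analysis set or denominator, and the consent provisions disagree with one another.

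Under the stated assumptions (emergencies 5–10% of cases, 20–30% of them failing, half of those failures unsigned, true success 89%), the false-pass probability on effectiveness is 7.4–15.4% against 4.9%. These are illustrations, because the documents give none of the three shares. The fragility figure needs no such share: at 204/217, four unseen failures are enough to lose significance.

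The documents do not support saying that outcome selection has occurred, or that it would reach tens of percent of all failures. The case for acting is that the remedy is cheap and that non-signers not tallied during enrolment may not be recoverable later.

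**What to change.** 1. **Tally (Protocol 11.2, with a matching exception in 11.4, as ethics committees allow).** Keep an anonymous count of every procedure in a site's enrolment period at which a MANTIS clip is selected: date, Group A–E, consented yes or no, and reason if not. Hold no outcome data. Report enrolled over eligible by site.
2. **Reconcile the consent sections.** Align 9.1, 10.1 and 11.4 with Section 20 on who may consent and when a subject counts as enrolled. Require that every such patient or representative is approached whatever the clip result. Do not add a consent cut-off.
3. **Analysis (eCRF and SAP Section 5).** The consent signature date is already collected; add a flag for consent before or after the procedure, which same-day cases need. Report both primary endpoints by consent timing. Add a sensitivity analysis that counts tallied non-signers as failures, labelled as a worst-case bound because their outcomes are unknown. State that the pre-procedure-consent subset differs in case mix and has less power, so a difference between subsets would not isolate consent bias.

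**Cost.** Protocol and SAP wording, one eCRF flag, a small burden on sites, and a sensitivity figure less favourable than the primary one. The 217 analysed and 240 enrolled are unchanged.
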